Appendix C – Baseline Questionnaire

ID				
	
JABATAN KESIHATAN PERGIGIAN MASYARAKAT DAN PENCEGAHAN KLINIKAL
 
Cross-Cultural Adaptation of a Betel Quid Cessation Program and Evaluation of Its Effectiveness in A Malaysian High-Risk Community
 
[name] [name], [name]. [name], Associate [name]. [name]
			
BASELINE QUESTIONNAIRE			Office use	

Date of Program: _____
 
Name (as in Identity Card): _____
 
Address (current home address): _____ _____
 
Telephone No.: _____
 
Identity Card No.: _____
				

SECTION A: DEMOGRAPHICS Please answer all the questions in the given space or tick (✓) in the given box
				

Participant's Information:
 
1. Age (as on last birthday): _____
 
2. Gender
 
a. Male 
 
b. Female 
 
3. Ethnic:
 
a. Malay 
 
b. Chinese 
 
c. Indian 
 
d. Bajau 
 
e. Dusun 
 
f. Irranun 
 
g. Others, please specify: _____ 
				

4. Marital Status

- a. Single
- b. Married
- c. *Widow/ Widower/ Divorcee*

5. Highest level of education

- a. Degree equivalent or higher
- b. Diploma or equivalent
- c. Certificate or equivalent
- d. STPM/ Matriculation or equivalent
- e. SPM or equivalent
- f. PMR or equivalent
- g. Primary school
- h. No formal education

6. Occupation

- a. Government or semi government employee
- b. Private employee
- c. Self employed
- d. Unpaid worker or home maker
- e. House maid

7. Individual's monthly income

- a. < RM 500
- b. RM 501 – RM 999
- c. RM 1000 – RM 2999
- d. RM 3000 - RM 4999
- e. RM 5000 and above

**SECTION B: CHEWING BEHAVIOUR & OTHER CONCOMITTANT RISK HABITS
(Maling TH & Doss JG, 2016)**

The section aims to determine the current chewing behavior, other concomitant risk habits and consequence of chewing behavior (medical conditions) of the betel quid chewers


1. What is your current betel quid chewing status?
 
a. No such habit (proceed to Q9)
 
b. Habit currently practiced
 
c. Past-habit and now has stopped
	

 

 

	

 
B1

2. At what age did you start chewing betel quid?
	
 Years old
	

 
B2

3. If you are an ex-chewer, how long ago have you stopped chewing betel quid?
 
a. A month ago
 
b. 3 months ago
 
c. About a year ago
 
d. Already more than 5 years
	

 

 

 

	

 
B3

4. For current chewer, how often do you chew betel quid?
 
a. Daily
 
b. 2-3 times a week
 
c. Few times a month
 
d. I am an occasional betel quid chewer
 
e. Others, please specify: _____
	

 

 

 

	

 
B4

5. How many quid(s) do you chew in a day?
	

	

 
B5

6. Do you keep the betel quid in your mouth overnight?
 
a. Yes
 
b. No
		

 
B6

7. Have you tried to quit chewing habit before?
 
a. Yes
 
b. No
	

 

	

 
B7

8. If you have tried quitting the chewing habit before, how many times did you tried?
	

	

 
B8

9. What is your current smoking status?
 
a. No such habit (proceed to Q11)
 
b. Habit currently practiced
 
c. Past-habit and now has stopped
	

 

 

	

 
B9


10. For current smoker, how often do you smoke cigarette?
 
a. Daily
 
b. 2-3 times a week
 
c. Few times a month
 
d. I am an occasional smoker
 
e. Others, please specify: _____
	

 

 

 

	

 
B10

11. What is your current alcohol drinking status?
 
a. No such habit (proceed to Q13)
 
b. Habit currently practiced
	

 

 

	

 
B11

c. Past-habit and now has stopped	
12. For current drinker, how often do you drink alcohol? a. Daily b. 2-3 times a week c. Few times a month d. I am an occasional drinker e. Others, please specify: _____	    
13. Do you have any medical condition (s)? a. Yes (Please specify): _____ b. No	 

SECTION C: BETEL QUID COMPOSITION PROFILE (Tahir Z., Doss JG & Jaafar N, 2003)

The section aims to assess the betel quid composition practiced by the chewers

1. What is (are) the ingredients that you use in your betel quid? a. Areca nut b. Tobacco c. Betel leaf d. Lime e. Gambir f. Others (If yes, please specify: _____)	      
--	--

SECTION D: REASONS FOR BETEL-QUID CHEWING SCALE (RBCS) (Little MA et al., 2014)

The section aims to assess the reasons the chewers chew betel quid

1. Did you began chewing betel quid because of the following:	Yes	No	
a. You like the taste			 D1
b. You like to have something in your mouth at all times			
c. All of your friends chew			
d. Your family members chew			
e. It's rude not to chew			
f. People will not respect you if you do not chew			
g. It relaxes you			
h. It gives you energy			
i. It helps you make decisions			
j. You like the way it makes you feel			
2. Which of your other family members that chews betel quid? (Only for those who answered 'Yes' for 1d)			
a. Children			 D2
b. Brothers			
c. Sisters			

d. Parents						
e. Grandparents						
f. Aunts						
g. Uncles						
h. Other family members						
3. Is it considered an insult if you do not chew betel quid in social situations?						
a. Never						 D3
b. Seldom						
c. About Half the Time						
d. Usually						
e. Almost always						
4. How important is chewing betel quid in the following situations:						
	Not important	Slightly important	Moderately important	Important	Extremely important	 D4
a. Birthdays						
b. Fiestas						
c. Anniversaries/deaths						
d. Parties						
e. Working						

SECTION E: BETEL QUID DEPENDENCY SCALE (T.A. Herzog et al., 2014)

The section aims to assess the betel quid dependency level among the chewers

1. Have you ever felt that you cannot go on without betel quid?						
a. Yes						 E1
b. No						
2. Have you found yourself having trouble stopping chewing betel quid once you started?						
a. Yes						 E2
b. No						
3. Have you ever chewed betel quid non-stop?						
a. Yes						 E3
b. No						
4. Have you experienced a strong craving for betel quid after you reduce or completely stopped chewing betel quid?						
a. Yes						 E4
b. No						
5. Whenever you want to chew betel quid but it is not available, would you spend a lot of time to find it?						
a. Yes						 E5
b. No						

6. Whenever you want to chew betel quid but it is not available, would you take extra steps and travel a great distance trying to buy it? For example, even suffer from fatigue by a long journey
 
a. Yes 
 
b. No 
	 E6

7. Have you felt agitated, irritated, or anxious after you reduce or completely stopped chewing betel quid?
 
a. Yes 
 
b. No 
	 E7

8. Have you experienced difficulty in concentrating or focusing after you reduce or completely stopped chewing betel quid?
 
a. Yes 
 
b. No 
	 E8

9. Have you experienced depression or drowsiness after you reduce or completely stopped chewing betel quid?
 
a. Yes 
 
b. No 
	 E9

10. Do you have a situation that the amount of betel quid is gradually increased every time you chew it from the first time you experienced it?
 
a. Yes 
 
b. No 
	 E10

11. Have you felt the need to increase the amount of betel quid chewing periodically in order to achieve a pleasant or refreshing effect?
 
a. Yes 
 
b. No 
	 E11

12. Have you often found yourself chewing more betel quid than expected and/or spending more time chewing betel quid than expected?
 
a. Yes 
 
b. No 
	 E12

13. Would you continue chewing betel quid if you find your teeth loosened or wiggled?
 
a. Yes 
 
b. No 
	 E13

14. Would you continue chewing betel quid if you have sensitive teeth (to hot or cold food)?
 
a. Yes 
 
b. No 
	 E14

15. Would you continue chewing betel quid if you experience canker sores or mouth ulcers?
 
a. Yes 
 
b. No 
	 E15

16. Have you reduced or given up any of your social, work, or leisure activities because of betel quid chewing?
 
a. Yes 
 
b. No 
	 E16

**SECTION F: READINESS & SELF PERCEIVED BARRIERS TO QUIT CHEWING HABIT
(Maling TH & Doss JG, 2016 & Brown RA, 2003)**

The section aims to assess the readiness and self-perceived barriers of chewers to quit their betel chewing habits

1. What is your readiness to quit your betel quid chewing habit now?
 
a. Have great determination to quit and thinks will succeed
 
b. Will reduce or modify habit
 
c. Attempted to quit but does not think it will succeed
 
d. Will continue and accept the consequences
	   	 F1

2. What are your barriers in quitting betel quid chewing habits?
 
a. Without BQ, I will be anxious
 
b. Without BQ, I will feel down, sad and depressed
 
c. Without BQ, I will feel easily irritable
 
d. Without BQ, I will gain weight
 
e. Without BQ, I will not be respected in my community/family
 
f. Without BQ, I will lose my social circle
 
g. It's hard to quit, I have tried in the past
 
h. I have thoughts to quit but I don't know how to quit
 
i. I don't think it is important to quit
 
j. Other, please specify: _____
	         	 F2

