1.6.2 Objectives of the study

- i. To determine the demographics of BQ chewers, BQ chewing behaviours, BQ composition and BQ dependency levels among its users in a high risk community in Malaysia
- ii. To determine the reasons for BQ chewing, the readiness and self perceived barriers to cease BQ habit among users in a high risk community in Malaysia
- iii. To adapt a BQ cessation program for a Malaysian high risk community
- iv. To evaluate the effectiveness of the adapted BQ cessation program through :

- a) self-reported cessation rates
- b) salivary biomarkers measurements

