2.3 Reasons for Betel Quid Chewing

To date, there is **no published study** on the assessment of reasons for BQ chewing in Malaysia. There was an unpublished study participated by Universiti Malaya (Herzog T et al., 2014) that stated ‘friends’ and ‘family’ were the greatest influence for Malaysians to commence BQ habits (42.2% and 32.3% respectively). Another reason was ‘readily available BQ around the house’ (9.3%) promoted the said behaviour.

More than half stated that the reasons they kept their BQ chewing practise were due to the influence of ‘most of their friends that chewed’ (54.7%), ‘they liked the taste’ (53.1%) and ‘they liked having something in the mouth’ (51.2%). Others claimed having kept the habit ‘as part of their culture’ (47.2%) and claimed ‘people did not respect them if they didn’t chew BQ’ (8.5%). The participants too added ‘chewing BQ was an important social event’ when hanging out with friends (40.5%), at home with family (37.1%) and in weddings (33.6%).

In Tahir Z et al. (2003), the authors found most of the villagers in Kampung Siasai, Kota Belud (n=175) practised BQ chewing mostly due to ‘the good feeling’ it gives chewers (59.8%) and for ‘socialising’ (51.4%). Other reasons noted by the authors were ‘for fun’ (12.6%), as a ‘cultural norm’ (12%), ‘as part of personal beauty and cravings’ (2.9%) and for ‘strengthening their teeth’ (1.7%).

In 2014, Little MA et al. developed **Reasons for Betel-Quid Chewing Scale (RBCS)**; a standardized instrument to assess the reasons why individuals chew betel-quad. There was 3 domains to assess the reasons for chewing: namely **reinforcement**,

social/cultural, and stimulation. The reasons portrayed in Herzog T et al. (2014)'s unpublished study were the few items comprised in the first and second domains for this scale.

Murphy KL et al. in 2022 concluded that the RBCS was a valid and reliable tool to measure the reasons for chewing BQ across different genders and different type of chewers as its items were moderately and strongly correlated to each other.

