Number of past quit attempts	The number of attempts participants have tried to cease the behaviour in the entire lifetime	Continuous/ Numerical	
Current Smoking Status	Did the participant smoke at least 1 cigarette for the past 1 week	Categorical	0- No such habit 1- Habit currently practised 2- Past habit and now has stopped
Frequency of smoking	How often does the current smoker smokes	Categorical	1- Daily 2- Two-three times a week 3- Few times a month 4- I am an occasional smoker 5- Others, please specify
Current Drinking Status	Did the participant drink at least 1 pint of alcohol for the past 1 week	Categorical	0- No such habit 1- Habit currently practised 2- Past habit and now has stopped
Frequency of alcohol drinking	How often does the current alcohol drinker drinks	Categorical	1- Daily 2- Two-three times a week 3- Few times a month 4- I am an occasional drinker 5- Others, please specify
Medical problems	Medical conditions of the participant	Categorical	1- Yes (specify) 2- No

Part C – BQ Composition (Tahir Z & Doss JG, 2003)

Conceptual Definition	Operational Definition	Type of Variable	Scale of Measurement
Betel quid composition	The composition of BQ chewed by participants	Categorical	a. Areca nut b. Tobacco c. Betel leaf d. Lime e. Gambir f. Others (please specify)

Part D – Reasons for betel-quid chewing scale (RBCS) (Little MA et al., 2014)

Conceptual Definition	Operational Definition	Type of Variable	Scale of Measurement
Construct 1: Reinforcement			
1. I like the taste	Participants chews BQ because they enjoy the quid's taste	Categorical	0 = No 1 = Yes
2. I like to have something in my mouth at all times	Participants chews BQ because they are fond of having something in the mouth at all time period	Categorical	0 = No 1 = Yes
Construct 2: Social/cultural			
3. All of my friends chew	Participants chews BQ because all of their friend circle chews it as well	Categorical	0 = No 1 = Yes
4. My family members chew	Participants have family members who chews BQ (children, brothers, sisters, parents, grandparents, aunts, uncles, and other family members)	Categorical	0 = No 1 = Yes

5. It's rude not to chew	Participants chews BQ because it was considered rude or an insult if they didn't	Categorical	0 = No 1 = Yes
--------------------------	--	-------------	-------------------

6. People will not respect me if I don't chew	Participants chews BQ for respect from surrounding social circle	Categorical	0 = No 1 = Yes
---	--	-------------	-------------------

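### The one stem over all ten reasons-scale items asks why participants began chewing, while the section's aim and the variable definitions concern why they chew, so answers will mix the two

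*Protocol*

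**What the plan says.** The protocol speaks to this point in five places. Section letters follow Appendix C and section 3.15.1; section 3.10.1.1 lists the reasons section as E.

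- **Objective.** Section 1.6.2, objective ii: "To determine the reasons for BQ chewing, the readiness and self perceived barriers to cease BQ habit among users".
- **The scale.** Section 2.3 presents it as a standardised tool for why individuals chew, with three domains: reinforcement, social/cultural and stimulation.
- **Definitions.** Section 3.15.1, Part D, gives each item an operational definition. Two examples are "Participants chews BQ because they are fond of having something in the mouth at all time period" and "Participants chews BQ because all of their friend circle chews it as well".
- **Questionnaire.** Appendix C, Section D, opens with "The section aims to assess the reasons the chewers chew betel quid". The question that follows, with items a to j beneath it, is "Did you began chewing betel quid because of the following".
- **Reporting.** Section 3.15.2 plans percentages for individual items and a mean and standard deviation for each aggregated domain score.

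**The concern.** The stem asks about an event in the past, the start of the habit. The section heading above it, the description of the scale and the definitions in Part D all concern the habit as it is now. An analyst working from Part D would label the resulting variables as reasons for chewing, although the question put to participants was why they began.

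The conceptual framework (section 2.12) names reasons for chewing among the determinants of a participant's ability to quit. For a cessation programme the useful information is what keeps people chewing. Answers that blend starting and continuing cannot be separated afterwards, because the form does not record which question the participant had in mind.

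**Working it through.** No sample size, rate or test enters here, so the check sets the passages side by side.

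**1. How much of the scale is affected.** Items a to j in Appendix C, Section D, question 1, correspond to items 1 to 10 in Part D. All ten sit under the one stem. The Part D definitions divide as follows:

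| Part D items | What the definition describes |
|---|---|
| 1, 2, 3, 5, 6 | a reason, with the main verb in the present tense (participants chew because, or for) |
| 4 | a present circumstance: having family members who chew |
| 7, 8, 9, 10 | a present effect or feeling from chewing: relaxation, energy, help with decisions, liking the feeling |

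That is 5 + 1 + 4 = 10 items across all three domains. None is defined as a reason for starting.

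**2. Whether the two ideas differ in the protocol's own terms.** Section 2.3 reports one Malaysian survey in two parts. Influences to commence were friends, family and quid being available at home. Reasons the habit was kept included friends who chew, taste, having something in the mouth, and culture. The protocol therefore treats starting and continuing as separate.

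**3. Whether the two time points differ for participants.** Section 3.8 requires chewing over the past 6 months. For every eligible participant, the start and the present are at least that far apart.

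**4. How the answers would come out.** The stem is in the past tense, but the options are in the present: that the participant likes the taste, that it relaxes them, that it gives them energy. Options about help with decisions or liking the feeling describe effects learned by chewing and fit poorly as reasons for starting. A participant may follow the stem or the option. The recorded yes or no is the same either way, so the mix cannot be identified.

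**5. Whether another item supplies current reasons.**
- Question 2 of Section D (which relatives chew) goes only to those who say yes to item d, so it inherits the ambiguity.
- Questions 3 and 4 (whether declining is an insult; importance at social occasions) are in the present tense and unaffected, but Part D places them under Others, outside the three constructs.
- Section F asks about readiness and barriers to quitting.
- The follow-up questionnaire (Appendix M) asks about status, frequency, quids per day and ingredients, with no reasons.
- The trigger logs (Appendix D) record mood and activity at each chew, in the intervention arm only.

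None of these replaces the ten items.

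**The case against.** The strongest reply is that Appendix C is a draft with several checks ahead. Section 3.10.1.4 has experts judge items for clarity and for fit with the study's objectives. Section 3.10.2.1 adds cognitive debriefing, section 3.10.2.2 a pilot with a reliability check, and section 3.14.1 a review of each item with the facilitators. The ungrammatical stem looks like a slip, and items that sit oddly under it are what debriefing should expose. This lowers the risk that the stem reaches the field. It does not remove the contradiction as written, and nothing in those steps points to this stem.

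It can also be said that objective ii is a noun phrase without a tense, and that section 2.3 covers starting and continuing under one heading. That is correct. The conflict therefore rests on the stem against the section's own aim, the description of the scale and Part D, rather than on the wording of objective ii.

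A reader might infer more, and the protocol does not support it:

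- **That the data will answer a wholly different question.** The options, the section aim and the face-to-face interviews all pull towards current reasons. Mixed answers are the likelier result.
- **That item percentages would shift by 10 points or more.** The survey in section 2.3 gives friends as 42.2% for commencing and 54.7% for continuing, a gap of 12.5 points. The commencing figures total 42.2 + 32.3 + 9.3 = 83.8%, which would fit a single-choice question. The continuing figures total 54.7 + 53.1 + 51.2 + 47.2 = 206.2%, so that question must have allowed several answers. The friends options are also worded differently. The gap cannot be attributed to starting versus continuing.
- **That scores would not be comparable with the validated scale.** The scale's original stem is not in the protocol, so this cannot be checked.
- **That answers would be decades-old recall.** That is inferred from age. No typical starting age is given for this population, and Table 2.2 puts 10.7% of Malaysian female chewers as users of two years or less.

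**Conclusion.** The inconsistency is real and internal to the protocol. It covers the whole scored scale: ten of ten items and three of three domains. If the stem is used as printed, the answers will be an unidentifiable mix of starting and current reasons, reported under objective ii as reasons for chewing. The size of any distortion cannot be estimated from the protocol.

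The reach is limited. Objective ii is descriptive; the self-reported cessation outcomes, the salivary biomarkers, the hypothesis and the sample size do not depend on these items. The point should be corrected, but it does not threaten the trial's main question. The conclusion assumes that Appendix C is the text to be validated and translated, and that participants will not all read the stem the same way.

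**What to change.** Reword the stem in Appendix C, Section D, question 1, so that it asks why participants chew now, for example *Do you chew betel quid because of the following*. This brings it into line with the section's stated aim and with Part D. If reasons for starting are also of interest, add them as a separate question, score it separately, and give it its own entry in Part D.

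The cost is one line of the English questionnaire if it is changed before the validation and translation steps, which the timetable in section 3.25 places ahead of the pre-test and field work. After baseline interviews the current reasons could not be recovered from the recorded answers.

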3.4 Sample Size

The sample size needed for this study will be calculated from a previous study performed by Herzog TA et al. (2022). The sample size was calculated using OpenEpi Version 3 software with the following assumptions:

 Margin of error (α error)	:	0.05
 Power of study ($1-\beta$)	:	0.8
 Allocation Ratio	:	1
 Percent of Exposed with Outcome	:	38.64 %
 Percent of Unexposed with Outcome	:	9.09 %

A total of 76 participants are needed for this study and 38 participants in each arm. After calculation of 20% dropout at 22th day and in 3 months (16 people), a revised total of 92 participants are needed for this study with 46 participants in each arm (Figure 3.1)

[figure not shown]

[figure not shown]
Figure 3.1 Flow of the Participant Allocation in the Study

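### The question on which relatives chew is asked only after a reason-for-starting item, while the codebook defines family chewing as a fact, so it is under-recorded by an unknown amount

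*Protocol*

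**What the plan says.** Three places in the Protocol bear on this.

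- **Appendix C, Section D, question 1.** Ten Yes/No items sit under the stem "Did you began chewing betel quid because of the following". The fourth is "d. Your family members chew".
- **Appendix C, Section D, question 2.** The form then asks "Which of your other family members that chews betel quid? (Only for those who answered 'Yes' for 1d", with tick boxes for eight types of relative, starting with children.
- **Section 3.15.1, Part D (codebook for the same scale).** Item 4, in the social/cultural construct, is defined as "Participants have family members who chews BQ (children, brothers, sisters, parents, grandparents, aunts, uncles, and other family members", scored 0 for No and 1 for Yes. The friends item just above it is defined differently: "Participants chews BQ because all of their friend circle chews it as well".

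Section 3.15.2 plans percentages for individual items and a mean and standard deviation for each aggregated domain score. Objective ii in Section 1.6.2 is to determine the reasons for chewing.

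**The concern.** Question 1d is causal: a truthful No means that family chewing was not why the participant began. It does not mean that no relative chews. Question 2 is factual. Making the fact conditional on the cause loses it for everyone who has chewing relatives but began for another reason. The codebook then treats the variable as the fact, so for those people the form and the codebook give different values.

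At stake are the item 4 percentage, the social/cultural domain score that contains item 4, and the list of which relatives chew. Family chewing is relevant background here. Section 3.10.3.1 advises chewers to attend with family members who also chew, and Section 2.7 describes family support for chewing as a barrier to quitting. No analysis plan can restore answers that were never collected.

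**Working it through.** The plan gives no figure of its own on this point, so there is none to reproduce. The defect follows from the text alone; arithmetic serves only to show how far its size could vary.

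**Step 1. Follow the form for each kind of participant.**

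| Relatives chew | Began for that reason | Answer to 1d | Asked question 2 | Value from 1d | Value under codebook item 4 |
|---|---|---|---|---|---|
| Yes | Yes | Yes | Yes | 1 | 1 |
| Yes | No | No | No | 0 | 1 |
| No | not applicable | No | No | 0 | 0 |

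The form and the codebook disagree in the second row. A 0 in the data cannot be split into rows two and three.

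**Step 2. Is the fact recorded elsewhere?** No other item in Sections A to F of the baseline questionnaire asks about chewing by relatives, and neither does the follow-up form in Appendix M. What is skipped at baseline is not recovered.

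**Step 3. How many would be asked question 2?** Section 3.4 states that "a revised total of 92 participants are needed for this study with 46 participants in each arm". Let s be the share answering Yes to 1d. The number asked is 92 × s and the number skipped is 92 × (1 − s).

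| s (assumed) | Asked | Skipped |
|---|---|---|
| 32.3% | 29.7, about 30 | 62.3, about 62 |
| 50% | 46 | 46 |
| 70% | 64.4, about 64 | 27.6, about 28 |
| 90% | 82.8, about 83 | 9.2, about 9 |

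**Step 4. Does the Protocol fix s?** No. The nearest figure is in Section 2.3, where friends and family "were the greatest influence for Malaysians to commence BQ habits (42.2% and 32.3% respectively". That comes from an unpublished study, not this trial. The shares listed for starting add to 42.2 + 32.3 + 9.3 = 83.8%, under 100%, which is what a choose-one question could give. Item 1d is one of ten separate Yes/No items, so several can be ticked. In the same section the three leading reasons for continuing add to 54.7 + 53.1 + 51.2 = 159.0%, so they overlap, and each exceeds 50%. The share on 1d could well be above 32.3%.

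**Step 5. How many would be coded wrongly against the codebook?** Let f be the share with chewing relatives, and assume that everyone answering Yes to 1d has one. The number in row two of Step 1 is 92 × (f − s). The Protocol gives neither f nor s for this trial, so this number is unknown.

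**Step 6. Effect on the domain score.** The social/cultural construct has four items (3 to 6). If the aggregated score is a simple sum, which is an assumption, each row-two participant scores one point of four lower than the codebook definition implies.

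**The case against.** The strongest reply is that the skip is coherent. Section D is headed as a reasons scale, so question 2 can be read as a follow-up to those who name family as a reason. Codebook item 4 may simply have lost the causal wording its neighbours carry. On that reading a 0 correctly means that family was not a reason, and nothing is miscoded. This is plausible, and the fix below adopts it for item 4. But the codebook does not say it. As written it states a fact and repeats the relatives listed in question 2, so the form and the codebook still need reconciling.

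Two other objections stand in part. The presence of children on the list does not prove that question 2 was meant to measure exposure, since children who chew could be a reason for continuing; the point does not depend on it. Content validation, a pre-test and a pilot come before fielding (Sections 3.10.1.4 and 3.10.2), but a clearly worded skip instruction could pass a check for clarity.

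A reader might infer that family chewing will be recorded for only a minority, with about 62 of 92 never asked. The documents do not support this: it carries 32.3% over from another study and another kind of question. Item 1d also gives everyone a Yes/No value; what is lost after a No is the list of relatives. A reader might also infer harm to comparisons between villages, but none is planned for family chewing, and Section 3.5 matches villages on location and number of chewers.

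**Conclusion.** The inconsistency is real, established by the text, and minor. A factual question is asked only of those who give a causal answer, while the codebook defines the variable as the fact. Family chewing is therefore under-recorded relative to the codebook definition, by an amount that depends on two shares the Protocol does not give. The table of 30 to 83 participants reached shows possible reach under assumed shares; it is not an estimate.

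The consequence is limited to the item percentage, the social/cultural domain score and the listing of relatives under objective ii. The cessation outcomes in Section 3.12.1 and the biomarker outcomes in Section 3.12.2 do not use these items.

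**What to change.** 1. In Appendix C, Section D, remove the restriction on question 2, ask it of every participant, and add a None box.
2. In Section 3.15.1, Part D, define item 4 as family chewing being a reason for chewing, in line with the items around it.
3. List question 2 in the codebook as a separate exposure variable, Yes or No for each type of relative, outside the domain score.

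The cost is one line on the form, a small codebook edit and a few seconds more interview time. On the dates in Section 3.25, adaptation, pre-test and pilot come before fieldwork, so the change can be made before the form is used.
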